## **8.4 Overdose**

A maximum tolerated dose has not been established for osimertinib or savolitinib, therefore an overdose is any dose which exceeds the daily dose that is defined in this CSP.

- An overdose with associated AEs is recorded as the AE diagnosis/symptoms on the relevant AE modules in the eCRF and on the Overdose eCRF module.
- An overdose without associated symptoms is only reported on the Overdose eCRF module

If an overdose on an AstraZeneca study intervention occurs in the course of the study, the investigator or other site personnel inform appropriate AstraZeneca representatives immediately, but **no later than 24 hours** of when he or she becomes aware of it.

The designated AstraZeneca representative works with the investigator to ensure that all relevant information is provided to the AstraZeneca Patient Safety data entry site, within one or 5 calendar days for overdoses associated with an SAE (see Section 8.3.1) and within 30 days for all other overdoses.

## **8.5 Human Biological Samples**

Instructions for the collection and handling of biological samples will be provided in the study specific Laboratory Manual. Samples should be stored in a secure storage space with adequate measures to protect confidentiality. For further details on Handling of Human Biological Sample see [Appendix C](#).

Samples will be stored for a maximum of 15 years from the date of the issue of the CSR in

line with consent and local requirements, after which they will be destroyed/repatriated.

- Pharmacokinetic samples will be disposed of after the Bioanalytical Report finalisation or 6 months after issuance of the draft Bioanalytical Report (whichever is earlier), unless consented for future analyses.
  - Pharmacokinetic samples may be disposed of or anonymised by pooling. Additional analyses may be conducted on the anonymised, pooled PK samples to further evaluate and validate the analytical method. Any results from such analyses may be reported separately from the CSR.

### 8.5.1 Pharmacokinetics

- Plasma samples will be collected for measurement of plasma concentrations of osimertinib, savolitinib and their metabolites as specified in the SoAs (Table 1 and Table 2) and Table 10.
- Samples may be collected at additional time points during the study if warranted and agreed upon between the investigator and the sponsor, eg, for safety reasons. The timing of sampling may be altered during the course of the study based on newly available data (eg, to obtain data closer to the time of peak or trough matrix concentrations) to ensure appropriate monitoring.
- Samples will be collected, labelled, stored, and shipped as detailed in the Laboratory Manual.

**Table 10 Pharmacokinetic Sampling Schedule**

Cycle number	Sampling point a
Cycle 1, Day 1	Pre-dose, and 1 and 3 hours post-dose
Cycle 2, Day 1	Pre-dose, and 1 and 3 hours post-dose
Cycle 3, Day 1	Pre-dose, and 1, 3, 4, and 6 hours post-dose b
Cycle 6, Day 1	Pre-dose
Discontinuation	Discontinuation PK samples will be collected as soon as feasible if a patient discontinues due to an AE reaction.

a Samples may be collected at additional timepoints.

b Triplicate ECGs to be collected at these timepoints as described in Section 8.2.3.

PK sample collection windows are: Pre-dose, up to 2 hours pre-dose; 1 hour post-dose, ± 5 minutes; 3 hours post-dose, ± 10 minutes; 4 hours and 6 hours post-dose, ± 30 minutes.

PK samples are collected for both treatment periods. Timings are relative to the start of study intervention ie, randomised treatment or cross-over.

AE = Adverse event; ECG = Electrocardiogram; PK = Pharmacokinetics.

On PK days patients should come to the clinic fasted where they will first be given a moderate breakfast (the same breakfast should be given on all PK days) and will administer the

savolitinib and osimertinib/placebo dose at the same time. Fasting state will be collected in the eCRF. Pre-dose PK sample may be drawn up to 2 hours pre-dose (before or after breakfast).

Samples will be used to analyse the PK of savolitinib, osimertinib and their metabolites and appropriate PK parameters will be determined and summarised. Summary concentrations for appropriate PK parameters will be reported in the CSR separately for randomised and cross-over treatment. The concentration data from this study may be combined with data from other studies in a population PK analysis and, if conducted, will be reported separately from the CSR.

Any changes in the timing or addition of time points for any planned study assessments for individual patients must be documented and approved by the relevant study team member and then archived in the sponsor and site study files, and may not constitute a CSP amendment. The IRB/IEC will be informed of any safety issues that require alteration of the safety monitoring scheme or amendment of the ICF and CSP.

#### **8.5.1.1 Determination of Drug Concentration**

Samples for determination of individual drug and/or metabolite concentrations in plasma will be assayed by bioanalytical test sites operated by or on behalf of AstraZeneca, using an appropriately validated bioanalytical method. Full details of the analytical method used will be described in a separate bioanalytical report.

Drug concentration information that would unblind the study will not be reported to investigative sites or blinded personnel until the study has been unblinded.

Incurred sample reproducibility analysis, if any, will be performed alongside the bioanalysis of the test samples. The results from the evaluation, if performed, will be reported in a separate Bioanalytical Report.

#### **8.5.2 Immunogenicity Assessments**

Immunogenicity is not evaluated in this study.

#### **8.5.3 Pharmacodynamics**

Pharmacodynamic parameters are not evaluated in this study.

### **8.6 Human Biological Sample Biomarkers**

#### **8.6.1 Collection of Mandatory Samples for Biomarker Analysis**

By consenting to participate in the study the patient consents to participate in the mandatory research components of the study. The following samples for biomarker research are required and will be collected from all patients in this study as specified in the SoAs ([Table 1](#) and [Table 2](#)):

- Tumour specimen, taken following progression on prior treatment with osimertinib, will be required at Pre-screening to assess eligibility. The MET amplification status of the patients' tumour specimen by FISH will be determined at a central laboratory. This analysis is required to investigate the presence of MET gene amplification that is needed to include the patient in the study. CCI [REDACTED]  
[REDACTED] Tumour sample requirements for biomarker testing will be defined in the supporting Laboratory Manual.
  - Sampling should be undertaken by experienced physicians in appropriate medical facilities in accordance with standard clinical practice for patients with advanced NSCLC.
  - Patients will only undergo tumour specimen collection when the risks are considered medically acceptable by their caring physicians. Where possible, high-risk sites (such as brain, pancreas, etc) should be avoided.
  - Supported by NCCN/European Society for Medical Oncology guidelines, tumour re-biopsy at PD is an option for standard clinical practice at many sites in order to evaluate the appropriate therapeutic options, including in the event of alternative mechanisms of resistance to EGFR-TKI treatment.
- Blood samples will be collected at Pre-Screening and Screening to analyse plasma biomarkers. CCI [REDACTED]

CCI [REDACTED]

As the rate of clearance of ctDNA after 6-weeks of therapy is a secondary endpoint, these data will be presented in the CSR. The results of the other exploratory research may be reported separately from the CSR.

The results of this exploratory research may be pooled with data from other studies with the study interventions to generate hypotheses to be tested in future studies.

### 8.6.2 CCI [REDACTED]

CCI [REDACTED]

CCI [REDACTED]

**8.6.3** CCI [REDACTED]

CCI [REDACTED]

CCI [REDACTED]

**8.7** CCI [REDACTED]

CCI [REDACTED]

CCI [REDACTED]

CCI [REDACTED]

**8.8 Medical Resource Utilisation and Health Economics**

Medical resource utilisation and health economics are not evaluated in this study.

**9 STATISTICAL CONSIDERATIONS**

**9.1 Statistical Hypotheses**

The primary objective of this study is to assess the ORR of savolitinib in combination with osimertinib versus savolitinib in combination with placebo in patients with EGFRm+, MET amplified locally advanced or metastatic NSCLC who have progressed on previous osimertinib therapy. The null hypothesis is that there is no difference between treatment groups on ORR based on investigator assessment per RECIST 1.1 when all patients have had the opportunity to be treated for 6 months. The alternative hypothesis is that there is a difference between treatment groups in this regard.

## 9.2 Sample Size Determination

Prior to CSP V3.0, approximately 200 patients were planned to be screened to achieve 56 patients randomly assigned to study intervention, with the primary analysis to occur 6 months after the last patient was randomised. With 56 patients (28 per arm) planned, CCI

[REDACTED]. At least half of the patients in the study (28 patients) will be second-line patients who were treated with osimertinib in the first-line setting.

Under CSP V3.0, the planned number of randomised patients will not be met. This is a result of the decision by AstraZeneca to terminate study recruitment early.

### 9.3 Populations for Analyses

The following populations are defined:

**Table 11 Populations for Analysis**

Population/Analysis set	Description
Full Analysis Set	The FAS will include all randomised patients with treatment groups assigned in accordance with the randomisation, regardless of the treatment actually received. Patients who are randomised but did not subsequently receive treatment will be included in the FAS. The analysis of data using the FAS therefore follows the principles of intention to treat. The FAS will be the primary population for reporting efficacy data and to summarise baseline characteristics.
Safety Analysis Set	The SAS will consist of all randomised patients who received any amount of study intervention. If a patient receives any amount of an experimental therapy, they will be summarised in the treatment group corresponding to the first experimental treatment they received. The SAS will be used as the primary population for reporting safety data
Cross-over Analysis Set	The Cross-over Analysis Set will consist of all patients who crossed over to savolitinib plus osimertinib who have received at least one dose of savolitinib plus osimertinib. It will be used as the population for reporting the efficacy and safety data for patients who crossed over to treatment with savolitinib plus osimertinib following objective progression on savolitinib plus placebo.
PK Analysis Set	All patients who receive at least 1 dose of savolitinib or osimertinib as per the CSP, for whom there are at least one reportable PK concentration will be included in the PK Analysis Set.
Interim Futility Analysis Set	The Interim Futility Analysis Set will include the patients who have had the opportunity to be treated for 2 RECIST post baseline scans (12 weeks). This analysis set will only be used for the interim futility analysis.

CSP = Clinical Study Protocol; FAS = Full Analysis Set; PK = Pharmacokinetics; RECIST = Response Evaluation Criteria in Solid Tumours; SAS = Safety Analysis Set.

### 9.4 Statistical Analyses

Under CSP V3.0, the SAP will be finalised prior to the unblinding of the study that is to occur following early study recruitment termination, for the purpose of an early review of the study data by AstraZeneca.

The SAP will include a more technical and detailed description of the statistical analyses described in this section. This section is a summary of the planned statistical analyses of the most important endpoints including primary and key secondary endpoints.

#### 9.4.1 General Considerations

Descriptive statistics will be used for all variables as appropriate and will be presented by treatment arm. Continuous variables will be summarised by the number of observations, mean, standard deviation, median, minimum, and maximum. Categorical variables will be summarised by frequency counts and percentages for each category. Unless otherwise stated, percentages will be calculated out of the population total for the corresponding treatment arm.

Results of all statistical analyses will be presented using a 95% CI and p-value, unless otherwise stated.

Additional subgroup analyses of efficacy and safety may be performed and will be specified in the SAP.

Depending on the extent of any impact, summaries of data relating to patients diagnosed with COVID-19, and impact of COVID-19 on study conduct (in particular missed visits, delayed or discontinued study intervention, and other protocol deviations) may be generated. More detail will be provided in the SAP.

Baseline for patients on randomised treatment will be the last assessment of the variable under consideration prior to the intake of the first dose, except for efficacy variables. For efficacy variables, baseline is defined as the last visit prior to randomisation. For patients who cross-over from savolitinib plus placebo to savolitinib plus osimertinib, their data will be cut off for the purposes of any savolitinib plus placebo assessment at the last assessment of the variable under consideration prior to the intake of the first dose of the combination therapy.

Efficacy data will be summarised and analysed on the FAS, safety data will be summarised on the SAS and PK data will be summarised on the PK Analysis Set.

Baseline for ORR, PFS, DoR and tumour size assessments of patients who cross-over to savolitinib plus osimertinib from savolitinib plus placebo will be the progression scan on savolitinib plus placebo, acquired within 28 days of the start of treatment in the cross-over period. CCI

Baseline for safety assessments of patients who cross-over to savolitinib plus osimertinib from savolitinib plus placebo will be set as the last assessment prior to first dose of osimertinib.

A Cross-over Analysis Set is included for patients randomised to savolitinib plus placebo who cross-over to savolitinib plus osimertinib upon objective PD per RECIST 1.1.

##### 9.4.1.1 Stratification Factors

The stratification in the statistical analyses will be based on the values entered in the IWRS at randomisation, even if it is subsequently discovered that these values were incorrect. If there

are any patients who were mis-stratified, a sensitivity analysis on the primary endpoint may be carried out using the correct baseline data collected in the eCRF.

#### **9.4.1.2 Multiplicity Strategy for Primary and Key Secondary Endpoints**

Prior to CSP V3.0, the primary analysis was to occur 6 months after the last patient was randomised. This will be based on a comparison of the primary endpoint (ie, ORR) between treatment groups and will be tested at the 2-sided 5% significance level.

CCI [REDACTED] the secondary efficacy endpoints will be tested at a 2-sided significance level of 5%. There will be no adjustment for multiplicity as the study is not designed to support labelling claims on any of the endpoints.

Final analysis was to be performed after the earlier of 18 months after the last patient was randomised or when 70% of the patients have progressed or died due to any cause. CCI [REDACTED]

Under CSP V3.0, as a result of AstraZeneca's decision to terminate study recruitment early, there will be no primary analysis at the originally planned timepoint. Following early termination of study recruitment, an initial DCO will occur to allow an early review of data by AstraZeneca. A final DCO will occur 9 months after the last patient has been randomised, after which the final analysis will be performed. CCI [REDACTED]

#### **9.4.2 Efficacy**

##### **Investigator RECIST Based Assessments**

From the investigators review of the imaging scans, the RECIST tumour response data will be used to determine each patient's visit response according to RECIST 1.1. It will be used to determine the endpoints of ORR, PFS, DoR and tumour size change.

At each tumour assessment, patients will be programmatically assigned a RECIST 1.1 visit response of CR, PR, SD or PD depending on the status of their disease compared with baseline and previous assessments. If a patient has had a tumour assessment which cannot be evaluated, the patient will be assigned a visit response of NE (unless there is evidence of progression in which case the response will be assigned as PD).

Investigator-assessment of PD per RECIST 1.1 of patients receiving savolitinib plus placebo is required prior to cross-over to savolitinib plus osimertinib.

Please refer to [Appendix H](#) for the definitions of CR, PR, SD, PD and NE.

### **Central Review of RECIST 1.1 Based Assessments**

The BICR of radiological imaging data will be carried out using RECIST 1.1. All radiological scans for all patients (including those unscheduled visits, or outside visit windows) will be provided to the BICR. The imaging scans will be reviewed by 2 independent radiologists using RECIST 1.1 criteria and will be adjudicated if required. The independent reviewers will be blinded to study intervention. Blinded independent central review data will be used to determine endpoints: ORR and PFS as a sensitivity analysis.

Further details of the BICR will be documented in the BICR charter.

#### **9.4.2.1 Analysis of Primary Endpoint**

Objective response rate by investigator assessment in accordance with RECIST 1.1 is the primary endpoint for this study.

The ORR is defined as the proportion of patients with an investigator-assessed response of CR or PR by RECIST 1.1.

Data obtained up until progression, or last evaluable assessment in the absence of progression, will be included in the assessment of ORR. Patients who discontinue treatment without progression, receive a subsequent anti-cancer therapy (note that for this analysis radiotherapy is not considered a subsequent anti-cancer therapy) and then respond will not be included as responders in the ORR.

The ORR will be analysed using a logistic regression model adjusting for the stratification used in the randomisation. The results of the analysis will be presented in terms of an odds ratio (an odds ratio greater than 1 will favour savolitinib in combination with osimertinib versus savolitinib in combination with placebo) together with its associated profile likelihood 95% CI and p-value (based on twice the change in log-likelihood resulting from the addition of a treatment factor to the model).

If there are not enough responses for a meaningful analysis using logistic regression then a CMH test will be presented.

Summaries will be produced that present the number and percentage of patients in each treatment group with a tumour response (CR/PR).

A sensitivity analysis of the ORR will be performed based on the BICR assessment of disease progression by RECIST 1.1. Further sensitivity analyses will be described in the SAP.

Summaries will be produced that present the number and percentage of patients in each treatment group with a tumour response (CR/PR). Summaries will also be produced for ORR per BICR.

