### Number of Patients:

The study planned to randomise 56 patients, with at least half of the patients in the study (28 patients) being second-line patients who were treated with osimertinib in the first-line setting.

Under CSP V3.0, the planned number of randomised patients will not be met. This is a result of the decision by AstraZeneca to terminate study recruitment early.

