## 4.2 Scientific Rationale for Study Design

### 4.2.1 Rationale for Study Design

The expansion cohort Part B of the TATTON study demonstrated anti-tumour activity of osimertinib in combination with savolitinib (ORR 30%, 95% CI: 20, 43) in MET amplified NSCLC patients (confirmed centrally by FISH; MET gene copy  $\geq 5$  or MET/CEP7 ratio  $\geq 2$ ) who were treated with prior 3rd generation T790M-directed EGFR-TKI (Sequist et al 2020).

This Phase II study has been designed to analyse the individual contribution of savolitinib to the efficacy seen with the combination by assessment of ORR in patients with EGFRm+ and MET amplified, locally advanced or metastatic NSCLC who have progressed following treatment with osimertinib. This study will enrol patients who have received up to 3 lines of prior therapy, which must include osimertinib but could also include other EGFR-TKIs, chemotherapy or chemotherapy in combination with an immuno-oncologic agent.

[figure not shown]
[figure not shown]
Around 5% to 22% of patients who receive a 3rd generation EGFR-TKI develop MET amplification (Bean et al 2007; Engelman et al 2007; Sequist et al 2011; Ramalingam et al 2018). Hepatocyte growth factor receptor amplification provides a by-pass mechanism of resistance to EGFR-TKIs activating the phosphoinositide 3-kinase pathway. However, simply targeting the emergent MET amplification without maintaining control of the EGFR sensitising mutation has been demonstrated to be inadequate to suppress tumour growth inhibition in non-clinical models (Engelman et al 2007). In order to overcome resistance to EGFR-TKI, the EGFR must still be inhibited, and EGFR inhibition is required to maintain remission. Furthermore, literature data demonstrate that for cancers that start to progress on EGFR-TKIs, discontinuation of the EGFR-TKI can lead to an acceleration of PD

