## **6.3 Measures to Minimise Bias: Randomisation and Blinding**

Patient eligibility will be established before treatment randomisation. Once the eligibility of a patient has been confirmed, the investigator (or nominated assistant) should contact the IVRS/IWRS Centralised Randomisation Centre for allocation of randomised therapy.

All patients will be centrally assigned to randomised study intervention using an IVRS/IWRS. Before the study is initiated, the telephone number and call-in directions for the IVRS and/or the log in information and directions for the IWRS will be provided to each site. Patients will be randomised in a 1:1 ratio with stratification according to the number of prior lines of therapy (ie, osimertinib monotherapy as first line or  $\geq$  second line [which includes patients who received osimertinib monotherapy as first line therapy followed by chemotherapy or osimertinib monotherapy after chemotherapy]). If a patient withdraws from the study, then his/her enrolment/randomisation code cannot be re-used. Withdrawn patients will not be replaced.

It is recommended that patients commence study intervention as soon as possible after randomisation, and ideally within 3 days. Patients will complete treatments as specified above or until disease progression is confirmed, unacceptable toxicity occurs, withdrawal of consent, or another discontinuation criterion is met.

The IVRS/IWRS will provide to the investigator(s) or pharmacists the kit identification number to be allocated to the patient at the dispensing visit. Routines for this will be described in the IVRS/IWRS user manual that will be provided to each centre.

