## 9.5 Interim Analyses

Prior to CSP V3.0, a non-comparative interim futility analysis for the savolitinib plus placebo arm was planned to occur after 20 patients overall (10 per arm) had the opportunity to be treated for 2 RECIST post-baseline scans (12 weeks). The outcome of the interim futility analysis was to be as follows:

- Stop further enrolment into the study if no responses are observed
- If true rate = 5%, there is a 59.9% probability of observing no responses.
- If true rate = 10%, there is a 34.9% probability of observing no responses.
- If true rate = 43%, there is a 0.4% probability of observing no responses.

Recruitment was to continue during the interim futility analysis.

If the decision was made by the IDMC that the study was futile, no new patients were to be enrolled into the study and all randomised patients were to be unblinded and those randomised to savolitinib plus placebo were to be given the opportunity to cross-over to savolitinib plus osimertinib (see Section 4.1.2).

The SAP will describe the planned analyses in greater detail.

Under CSP V3.0, as a result of AstraZeneca's decision to terminate study recruitment early, the planned interim futility analysis will not be performed and there will be no requirement for data review by the IDMC. Alternatively, following the termination of study recruitment, an initial DCO will occur to allow an early review of the data by AstraZeneca. The study will be unblinded after completion of data cleaning activities on the initial DCO data, and patients on savolitinib monotherapy (savolitinib plus placebo) will be given the opportunity to cross-over to the savolitinib plus osimertinib arm. If the investigator believes patients are gaining clinical benefit and patients have not reported PD, patients may continue to receive savolitinib monotherapy. All patients will be followed until the final analysis.

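### The primary ORR p-value comes from a logistic likelihood-ratio test that runs above its two-sided 5% level at small counts, and the protocol does not define when CMH replaces it

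*Supplement*

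**What the plan says.** Section 9.4.2.1 of the protocol (Amendment 2, CSP V3.0) fits a logistic model for ORR adjusted for the randomisation stratum. It reports an odds ratio with a profile-likelihood 95% interval and a "p-value (based on twice the change in log-likelihood resulting from the addition of a treatment factor to the model"). That is a likelihood-ratio chi-square with one degree of freedom. The fallback reads "If there are not enough responses for a meaningful analysis using logistic regression then a CMH test will be presented". No count, zero-cell rule or decision-maker is given. The Synopsis repeats both sentences.

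Section 9.4.1.2 says that the ORR comparison "will be tested at the 2-sided 5% significance level". Section 6.3 gives the allocation: "Patients will be randomised in a 1:1 ratio with stratification according to the number of prior lines of therapy", a factor with two levels. Section 9.2 records the design size, "With 56 patients (28 per arm) planned", and the Synopsis says that "the planned number of randomised patients will not be met". Section 9.4 leaves technical detail to an SAP that is to be final before the study is unblinded.

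**The concern.** The likelihood-ratio p-value relies on a large-sample chi-square approximation, which can be poor when one or both arms have few responders. The protocol itself allowed for few. Section 9.5 considered low response rates in the savolitinib plus placebo arm, for instance "If true rate = 10%, there is a 34.9% probability of observing no responses" in 10 patients, and the sample is now smaller than planned.

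Two things are at stake. The nominal 5% level may not be delivered for the primary endpoint. And if the likelihood-ratio and CMH tests disagree on sparse tables, the wording of the switch decides whether the result is called positive.

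**Working it through.** **Inputs.** Two-sided 5% (section 9.4.1.2); 1:1 allocation and one two-level stratum (section 6.3); 28 per arm as the upper bound (section 9.2). The achieved number is not given, so 10, 15 and 20 per arm are assumptions.

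**The protocol's own figures.** P(no responder in 10) = (1 − p)^10. At p = 5%, 10% and 43% this gives 59.9%, 34.9% and 0.4%, which match section 9.5.

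**Three responders against none, n per arm, strata pooled.**

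- Likelihood ratio: G² = 2(l₁ − l₀), where l₁ = 3 ln(3/n) + (n − 3) ln(1 − 3/n) and l₀ = 3 ln(3/2n) + (2n − 3) ln(1 − 3/2n). At n = 20, G² = 4.40 and p = 0.036.
- CMH without continuity correction: (3 − 1.5)²/V, where V = n·n·3·(2n − 3)/[(2n)²(2n − 1)]. At n = 20, V = 0.7115, the statistic is 2.25/0.7115 = 3.16 and p = 0.075.

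| Per arm | LR p | CMH p | Fisher p |
|---|---|---|---|
| 10 | 0.030 | 0.067 | 0.21 |
| 15 | 0.034 | 0.073 | 0.22 |
| 20 | 0.036 | 0.075 | 0.23 |
| 28 | 0.037 | 0.078 | 0.24 |

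With two strata, 16 ways of placing the three responders were tried (5+5, 7+3, 8+7 and 14+14 per arm). The likelihood-ratio p was 0.004 to 0.037 in all of them. The CMH p was above 0.05 in 13, at 0.060 to 0.080. The other three have all responders in one small stratum: 0.0495 (5+5, either stratum) and 0.025 (7+3, the stratum of 3). Two against none is not significant by either test (pooled LR p 0.084 to 0.092).

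**Type I error.** All two-stratum tables were enumerated with the same response rate in both arms and both strata (5, 10, 15, 20, 30, 40, 43 and 50%), rejecting when the statistic exceeds 3.84. The table gives the maximum over these rates, with the rate at which it occurs.

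| Per arm (strata) | LR on every table | CMH if an arm has no responders, otherwise LR | CMH always |
|---|---|---|---|
| 10 (5+5) | 8.9% (ORR 20%) | 6.9% (30%) | 4.4% |
| 15 (8+7) | 8.2% (15%) | 6.0% (30%) | 4.5% |
| 20 (10+10) | 8.6% (10%) | 6.2% (30%) | 5.0% |
| 28 (14+14) | 7.9% (5%) | 5.9% (20%) | 5.3% |

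The excess is not uniform. At 10 per arm the likelihood-ratio test has size 1.4% at an ORR of 5% and 5.0% at 10%. At 15 per arm it is 5.4% at 40% and 5.0% at 50%.

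**How often the choice of test matters.** Take 30% for the combination, from the earlier study cited in section 4.2.1 ("ORR 30%, 95% CI: 20, 43"), against 5% or 10% for savolitinib plus placebo. The two tests then disagree at 5% in 16% or 12% of trials at 10 per arm, 10% or 6% at 15, and 4% or 3% at 20.

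**The case against.** The strongest reply is that the 8-9% figures ignore the protocol's own fallback. A table with an empty arm is the case that the CMH sentence seems written for, and much of the excess sits in such tables. With CMH used there, the size at an ORR of 5-10% is 0.3-1.7% at 10 per arm and 2.5-5.3% at 28. This stands, and the 8-9% should not be quoted as the error rate of the plan as written. It does not clear the test: 5.9-6.9% remains at an ORR of 20-30%, a range that includes the 30% reported for the combination.

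A reader might infer that 3 against 0 would be called significant. The documents do not support that. The fallback may well apply, so the most that can be said is that it could be.

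A reader might also infer that the plan has no trigger at all. A numeric rule is ordinary SAP content, the SAP is not shown, and section 9.4 has it settled before unblinding. Nor does the protocol say that the test is chosen with the counts in view. The choice of the likelihood-ratio test, however, is made in the protocol.

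The 5% statement sits in a paragraph that opens with the arrangements before CSP V3.0, and the text after the V3.0 final-analysis sentence is redacted, so how far formal testing continues cannot be seen. Section 9.4.2.1 still prescribes a p-value. Finally, this is a Phase II study that section 9.4.1.2 says is not meant to support labelling claims. That lowers the severity.

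**Conclusion.** The concern holds as a moderate one. The specified likelihood-ratio test exceeds 5% at small counts: up to about 8-9% if applied to every table, and up to about 6-7% with a sensible zero-arm fallback. Stratified CMH stays at or below 5.3% in the same scenarios. Most 3-against-0 tables fall on opposite sides of 5% under the two tests, and the protocol text does not say which test governs.

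It would be wrong to attribute this to early termination alone. At 28 per arm the likelihood-ratio size is already 7.8-7.9% at an ORR of 5-10%, and 3 against 0 gives p = 0.037. Fewer patients make disagreement between the tests more frequent, but the method had this weakness at the planned size.

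The figures assume 10 to 28 per arm, near-equal strata, a common response rate across strata, and CMH without continuity correction. A 7+3 split at 10 per arm gave the same peaks (8.9% and 6.9%).

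**What to change.** Before unblinding, state in section 9.4.2.1, the Synopsis and the SAP that the CMH test stratified by prior line, without continuity correction, is the single ORR p-value whatever the counts. Keep the logistic odds ratio as an estimate only, with an exact conditional or Firth-type interval if an arm has no responders, since the maximum-likelihood odds ratio is then zero or infinite. If the likelihood-ratio test is retained, the least that is needed is a written count or zero-cell rule for the switch, though about 6-7% would remain at the smallest size.

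The rule does not carry over to the subgroup analyses in section 9.4.2.1: within one prior-line stratum there is nothing left to stratify by, so the test there should be named separately. A Miettinen-Nurminen interval for the ORR difference and Clopper-Pearson intervals per arm for the whole full analysis set would be useful but are optional.

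The cost is wording and a slightly less favourable p-value. CMH is not a complete safeguard, because it can still reject at 3 against 0 when all responders fall in one small stratum.
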